3.3. Approach

3.3.a. Preliminary Studies: The investigative team has extensive experience conducting clinical trials in this dual diagnosis population. Staff members at both sites have extensive experience conducting research in this population. Four studies directly pertinent to the current proposal are discussed below.

Pilot Study 1: A 12-week randomized, placebo-controlled, add-on, trial of citicoline

Methods: 44 outpatients with BPD and cocaine dependence were randomized to citicoline (2000 mg/day) or placebo.

Results: Those who took placebo had 6.41 times greater odds of testing positive for cocaine at exit than those who took citicoline. Days of cocaine use decreased with citicoline treatment, but increased with placebo (Cohen's d=0.6, medium effect size). The citicoline group had significantly (p = 0.006) better performance on the Rey Auditory Verbal Learning Test (RAVLT), an alternative word list (declarative memory). The Stroop Color test (executive functioning, attention, impulsivity) showed greater improvement with citicoline than placebo (2.8 ± 7.4 vs. -1.1 ± 4.6, p=0.04, Cohen's d=0.6). Study completion rates were over twice as high with citicoline as placebo. Side effects scale scores were significantly lower with citicoline than placebo (8.9 ± 1.5 vs. 9.8 ± 1.5, p<0.001).

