Among participants with alcohol use disorder (in addition to cocaine), and active alcohol use at baseline (n=14), potentially meaningful changes in alcohol use and craving were observed. Citicoline-treated patients had a significant decrease in alcohol craving based on a 0-100 mm visual analogue scale (-28.7±31.3, p=0.05) while the placebo-treated group showed a much smaller decrease in alcohol craving (-1.9±66.4, p=ns). Despite modest baseline values, alcohol use decreased by 0.9 ± 1.4 days/week in the citicoline group as compared to only 0.4 ± 0.9 days/week with placebo. Heavy drinking days decreased by 0.9 ± 2.1 (p=0.04) days with citicoline as compared to 0.0 ± 0.6 with placebo. Drinks per drinking day decreased by 2.4 ± 11.3 with citicoline and 0.8 ± 2.6 with placebo. In the alcohol use group, RAVLT delayed recall performance increased by 12.4 ± 12.9 points with citicoline (p=0.04), but decreased by 1.8 ± 3.5 points with placebo (Cohen's d = 1.5, large effect size). Significance: Findings suggest reductions in both cocaine and alcohol use with citicoline. Memory improved with citicoline, particularly in those with alcohol use. Citicoline was safe and well tolerated, and was associated with better study retention than placebo.

Pilot Study 2: A 12-week, double-blind, placebo-controlled trial of citicoline add-on therapy in patients with BPD I disorder and cocaine abuse/dependence

Methods: 130 outpatients with BPD (depressed), cocaine dependence and a cocaine-positive urine at baseline were given citicoline or placebo add-on therapy to stable doses of mood stabilizers. Both groups received cognitive behavioral therapy and a contingency management plan of escalating payments for each urine sample provided. These payments were not related to whether the urine drug screen (UDS) was positive. **Results:** Among those with at least one post-baseline visit (n=60 citicoline, n=61 placebo) a group (f=4.5, df=1,1057, p=.0351) and group by time interaction (f=11.2, df=1,1057, p=.0009) was observed. Similar results were observed when imputing missing data as cocaine-positive [treatment group effect (p=.0222), treatment group by time effect (p=.0151)]. Completion rates non-significantly favored citicoline (71% vs. 57%).

In those with alcohol dependence, citicoline (n=33) showed a trend toward a greater decrease in days per week of alcohol use than placebo (n=37) (-3.67±4.11 days vs. -1.86±4.44 days, p=.084).

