At Stage 1, we will recruit 99 subjects (i.e., 33 subjects per arm) with 1:1:1 treatment allocation ratio, which provides clinically meaningful minimum *effect size of 0.25 between each treatment arm and placebo with* a two-sided test at the 5% level of significance. After review of interim data, an additional 100 subjects at 1:1 ratio will be recruited at Stage 2. If the effect size for *both* medications is at least 0.50 at interim analysis then we will have 81.4% power with 66 participants per arm and the study will continue with three treatment arms. To summarize: 1) If neither treatment has an effect size of at least 0.25 at interim analysis then the trial is discontinued. *This effect size was selected because it is a clinically meaningful value. Naltrexone has an average effect size of approximately 0.15-0.20 in clinical trials for alcohol dependence.*¹³³ *Thus, a useful new treatment for alcohol dependence should at least have a larger effect size than the standard treatment. This effect size of 0.25 is also an effect size at interim analysis that provides a reasonable likelihood of a significant difference from placebo at study completion assuming some increase in effect size as more participants are*

enrolled and the variance of the data decreases. 2) If one treatment has an effect size of at least 0.25 then the trial continues dropping the less effective treatment (two-arm study of one medication vs. placebo). 3) If both treatments have an effect size of at least 0.50 then neither treatment is dropped and the trial continues as a three-arm trial (both medications vs. placebo). This assumes that the DSMB assessment determines that the selected treatment(s) has an adequate safety and tolerability profile to continue the trial. We anticipate that the interim analysis will take place at approximately month 26 of the study. As an incentive to enroll quickly and avoid prolonging the study, we will mandate that an interim analysis take place by month 34 even if fewer than 99 participants have been enrolled. All interim analysis decisions will be made in consultation with the NIAAA program official and DSMB.

Statistical Methods:

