The primary analysis is to assess between-group differences in alcohol use measures including drinks per drinking day (primary outcome measure), heavy drinking days, and drinking days using Generalized Estimation Equations (GEEs) analysis with a site effect as a cluster. GEE model has been used in a prescription drug abuse treatment study with multiple site adaptive design (Weiss et al., 2010).¹⁰⁶ Point estimates of the difference in the average of the number of drinks per drinking day between treatment groups and their corresponding 95% confidence intervals will be obtained. A similar analysis will be used to assess exploratory aims 1 (mood), 2 (side effects), and 3 (craving). Length of time in the study in weeks will be compared between groups using Cox proportional hazards regression (SAS Proc PHREG). Assessments only obtained at baseline and weeks 6 and 12 (e.g. GGT, AST, ALT and CDT levels) or baseline and week12 (e.g. cognitive assessments, neurosteroid and choline levels) will be analyzed using analysis of variance (ANOVA). The correlation between the reduction in alcohol use/alcohol craving and reduction in manic and depressive symptoms, and also improvement in cognitive outcomes, will be assessed using Pearson's or Spearman's correlation coefficient. To address exploratory aim 6) "Determine whether changes in alcohol craving, mood or cognition occur before or after changes in alcohol use." a panel model with lagged effects¹³⁴ will be used to analyze 12-week longitudinal data (SAS Proc Panel) in order to explore serial correlations between changes in alcohol use and depressive symptoms or cognitive outcomes with lagged effect (e.g. one week, two week). The panel model will be constructed for each alcohol use, alcohol craving, depressive and manic symptom, and cognitive outcome and test if change in alcohol use follows changes in craving, mood or cognition at subsequent visits and vice versa.

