At each stage, a table will show the adverse events (categorized by seriousness, severity, and possible association with study drug) ordered by decreasing frequency for all patients. If appropriate, the incidence rate of adverse events will be compared by Fisher's Exact Test. Special attention will be given to those participants who have discontinued due to adverse events or experienced a serious adverse event. Exploratory analyses such as determining if baseline blood neurosteroid or choline levels predict response and whether changes in these levels are associated with clinical response will be conducted using a mixed model (SAS Proc GLIMMIX) with baseline blood neurosteroid and choline levels as fixed effects. In addition, subgroup analyses with respect to patient demographics and characteristics may be performed as deemed appropriate by the PI and/or biostatistician. Unless otherwise noted, tests of hypotheses are 2-sided and the nominal level of significance will be 0.05.

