3.3.d. Dropouts: Retention is challenging in studies involving BPD/schizoaffective disorder and substance dependence. We have greatly improved our retention over the years by implementing 1) more frequent visits, 2) more frequent contact to remind participants of appointments, and 3) the use of a psychosocial platform. To minimize attrition, we will obtain multiple contact numbers, pay participants small sums at each visit, and to the extent possible have the same research coordinator and psychiatrist assess participants at each visit. In addition, data will be analyzed using an analysis that uses all of the available data and allows for missing data. We will also use a contingency management strategy in which participants are given small vouchers that increase in value with consecutive appointments attended and reset following a missed appointment. We included a similar strategy in a recently completed study in BPD and cocaine dependence (Dallas site) and observed substantial improvement in retention. We anticipate that, using the above approach and considering completion rates in both PI's studies, the proposed study will have a completion rate > 70%. Although we will make every effort to minimize missing visits and dropouts, dropouts and missing visits are common in longitudinal studies. Therefore, we will do comprehensive sensitivity analyses to investigate the consequences of incomplete observations in the analysis of repeated measurement data using local influence, pattern mixture models and multiple imputations.¹³⁵⁻¹³⁷

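### The site-clustered primary GEE is not protected against dropout that depends on earlier drinking, and citicoline's retention history makes a biased citicoline comparison possible.

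*Combined protocol and SAP*

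**What the plan says.** Section 3.3.c (Statistical Methods) analyses drinks per drinking day "using Generalized Estimation Equations (GEEs) analysis with a site effect as a cluster". It names no working correlation within participant, no weighting and no missingness assumption. The quantity to be estimated is the between-group difference in average drinks per drinking day.

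Section 3.3.d covers the primary analysis in one clause: "data will be analyzed using an analysis that uses all of the available data and allows for missing data". It expects more than 70% to complete overall and gives no figure by arm. It then promises sensitivity analyses by multiple imputation, pattern-mixture models and local influence, without stating their assumptions, shift parameters or how they would alter a conclusion. Section 3.3.c also plans a Cox comparison of time in study.

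On earlier retention:
- Citicoline, Pilot Study 1 (n=44, cocaine): "Study completion rates were over twice as high with citicoline as placebo".
- Citicoline, methamphetamine trial in section 3.1.f (n=48): significantly better retention and more than double the completion of placebo.
- Citicoline, Pilot Study 2 (n=130, cocaine): 71% against 57%, reported as non-significant.
- Pregnenolone, Pilot Study 4 (n=80): retention similar to placebo. Pilot 3 gives no comparison.

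Section 3.3.c (Sample size re-estimation) stops the trial if neither drug reaches an effect size of 0.25 at interim, and keeps both only if each reaches 0.50. The General Analytic Plan applies the primary efficacy analysis at both stages, but no passage states how the interim effect size is computed.

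**The concern.** Using every available record differs from being valid when records are missing for a reason. An unweighted GEE is in general consistent when dropout is unrelated to the outcome given the modelled covariates. If dropout depends on drinking already observed (missing at random, MAR), the analysis must use each participant's earlier values to stand in for the later ones. A GEE clustered on site with nothing stated within participant is fairly read as working independence, which makes no such use of them.

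Dropout related to drinking is plausible here. The discontinuation criteria in section 3.3.b.3 include mood worsening, involuntary hospitalization, incarceration and significant alcohol withdrawal. In Pilot Study 2 the investigators themselves repeated the analysis with missing urines counted as positive.

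At stake is the citicoline-placebo estimate at the final test and, if the same estimator is used, at the interim. A bias that affects citicoline alone could also tilt which drug a drop-the-loser design keeps. A later sensitivity analysis cannot undo an arm already dropped.

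**Working it through.** **1. The plan's own figure.** The plan says that if the effect for both drugs "is at least 0.50 at interim analysis then we will have 81.4% power with 66 participants per arm". With two-sided alpha 0.05, the noncentrality is d√(n/2) = 0.50 × √33 = 2.87. The noncentral t with 130 df gives 81.35%, and the normal form Φ(2.87 − 1.96) gives 81.9%. The figure reproduces. The calculation has no term for dropout.

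**2. Pilot Study 2 retention.** With the post-baseline denominators (60 and 61), 71% is about 43/60 and 57% about 35/61. Fisher's exact p = 0.13, in line with the protocol's wording.

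**3. Mechanism.** Under independence the estimate is a contrast of observed visit means. If heavier drinkers leave, each arm's observed mean falls below its full-sample mean, and falls further in the arm that loses more people. If both arms lose equally through the same link, the shifts cancel. If loss is unrelated to drinking, there is no shift.

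**4. Size.** The model for dropout is logit P(leave at visit t) = α(arm) + log(OR) × drinking/SD, with α set to give the target completion. There were 60,000 per arm, 12 weekly visits and a unit-variance outcome (random intercept variance 0.4, with and without AR(1) 0.8). Simulation noise is about 0.01. The 71/57% split is Pilot Study 2's. The 80/40% split (one reading of over twice), the odds ratios and the correlations are assumptions. Estimates when the true effect is 0.50:

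| Completion, drug/placebo | Dropout link | Independence GEE | Exchangeable GEE by participant |
|---|---|---|---|
| 71/57 or 80/40 | none | 0.49-0.50 | 0.49-0.50 |
| 70/70 | previous or current drinking, either direction | 0.49-0.50 | 0.49-0.50 |
| 71/57 | heavier leave, previous visit, OR 1.5-2 | 0.45-0.47 | 0.49-0.50 |
| 80/40 | same | 0.37-0.44 | 0.49-0.50 |
| 71/57 | heavier leave, current unseen visit | 0.45-0.47 | 0.48-0.49 |
| 80/40 | same | 0.36-0.43 | 0.45-0.48 |
| 71/57 | lighter leave, OR 0.5-0.67 | 0.51-0.54 | about 0.50 |
| 80/40 | same | 0.54-0.63 | 0.49-0.52 |

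A second variance model (intercept SD 2.0, slope SD 0.25, residual SD 1.5), with odds ratios 1.5-3 and the same link in both arms, gives independence bias of about 0.02-0.07 SD at 71/57% and 0.08-0.17 SD at 80/40%. When dropout depends on observed drinking, exchangeable correlation by participant leaves about 0.00-0.03 SD. A likelihood model given the true covariance leaves less than 0.005 SD.

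**5. Power.** At 66 per arm (normal form), power falls from 82% at 0.50 to 73% at 0.45 and 57% at 0.37.

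**6. Interim.** Stage 1 has "99 subjects (i.e., 33 subjects per arm) with 1:1:1 treatment allocation ratio". The SE of an effect size is about √(2/33) = 0.246. A true 0.25 is estimated on average at 0.21-0.23 (71/57%) or 0.12-0.20 (80/40%) if heavier drinkers leave. Taking SE 0.25, the chance that citicoline reaches 0.25 is 1 − Φ((0.25 − mean)/0.25). This is 50% without bias, 44-47% at 71/57% and 30-42% at 80/40%.

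**The case against.** The strongest reply is that the bias needs two conditions together: unequal retention and a link between drinking and dropout. The documents establish the first only in part and do not quantify the second. The retention evidence concerns citicoline alone, comes from cocaine and methamphetamine samples, and is non-significant in the largest trial. All of this stands.

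A reader might infer that the GEE is unbiased only if dropout is unrelated to drinking. That is too strong, since equal retention or a near-correct participant-level correlation removes most or all of the bias in the table. A reader might also infer that both drugs' pilots show better retention, but pregnenolone's was similar to placebo. Nor must a drug that retains people look worse, because the sign reverses if lighter drinkers leave.

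Larger biases can be produced, about 0.04-0.19 SD for a week-12 contrast or 0.04-0.14 SD if the dropout link differs by arm. However, the plan's estimand is the average difference, and nothing in the documents supports an arm-specific link.

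The planned imputation and pattern-mixture analyses do answer part of the point at the final analysis. They do not answer it for the primary estimate, and nothing ties them to the interim rules. It is also true that the near-zero likelihood result used the true covariance. An unstructured 12-visit matrix has 12 × 13/2 = 78 parameters, a heavy demand with 99 participants.

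**Conclusion.** The point holds in a conditional form. As specified, the primary estimator is not generally valid when dropout depends on earlier drinking, and the assurance in section 3.3.d does not change that. For citicoline against placebo, with dropout odds ratios of 1.5-3 per SD and a link common to both arms, the bias is about 0.02-0.07 SD at Pilot Study 2's retention and 0.08-0.17 SD at 80/40%. Its direction is unknown. It is essentially zero if retention is equal or unrelated to drinking. The odds ratios, the correlation structures and the 80/40% split are assumptions.

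It would be tempting to say that the GEE sets the 0.25 and 0.50 decisions. The documents suggest this by applying the primary analysis at both stages, but they also describe a confidence-interval approach and never define the interim effect size. If the GEE is used, a true effect near 0.25 could be pulled below the cut-off. The interim SE of about 0.25 is larger than the bias, so chance dominates there. The bias, unlike the SE, does not shrink by the final analysis. This is a worthwhile, inexpensive improvement and does not invalidate the design.

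**What to change.** Make a participant-level, MAR-valid analysis primary, and state that it also supplies the interim effect size. Either of these would serve:

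- A likelihood repeated-measures model with treatment, visit, treatment-by-visit, baseline drinking and site, a named covariance structure and a simpler named fallback, since an unstructured matrix may not be estimable at interim.
- A GEE clustered by participant, run on the multiple imputations already planned.

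Keep pattern-mixture models as the sensitivity analysis for dropout that depends on unseen drinking, with the shifts by arm fixed in advance.

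The cost is SAP wording and programming, with no change to sample size or visits. The small downside is that the covariance structure and fallback must be pre-specified.

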3.4. Conceptual and Design Issues

Why was drinks per drinking day selected as the primary outcome measure? Analysis of findings from prior studies in this population by the PIs suggests this is the outcome measure most sensitive to medication effects in this group of dual diagnosis patients. Data in the literature suggest that dual diagnosis patients with alcohol use disorders may have somewhat different use patterns (e.g. lower overall use but greater disability from the use) than those with alcohol use disorders alone.¹³⁸ Thus, we use an outcome measure appropriate for the patient population investigated. Please note that other alcohol use measures will also be obtained.

Why use an adaptive design rather than a convention three-arm study? 1) It is consistent with the PA. 2) It allows for fewer participants, time, and resources by reallocating resources to the more promising treatment at interim analysis. A potential disadvantage is the risk of "throwing out the baby with the bathwater" by removing one treatment at interim analysis. We minimize this risk by 1) waiting until 99 participants have been enrolled before conducting the interim analysis, and 2) allowing for both treatments to remain should they both appear to be particularly promising at interim analysis. It is important to note that should a treatment appear relatively promising on some of the alcohol, mood or cognitive outcomes, but nonetheless be dropped due to the predetermined pruning rules, information obtained is still valuable as pilot data for additional research.

How might these medications be used in a regimen for BPD or schizoaffective disorder, bipolar type and AUD? With the exception of valproate⁵³, none of the mood stabilizers used for BPD or schizoaffective disorder, bipolar type have demonstrated efficacy for AUD. However, these medications have substantial side effect burdens (e.g. sedation, metabolic syndrome) and drug-drug interactions. Both of the medications proposed in this application appear to have very favorable side effect profiles and no known drug-drug interactions. In addition, both medications show promise for not only reducing alcohol use but possibly also improving mood and cognition. Thus, we suggest these would potentially be very safe and effective medications to add to existing medication regimens in a dual diagnosis population.

References

